22.6 SECONDARY ENDPOINTS

Secondary endpoints will be described in the SAP and will include:

- Immunological Response 2: Reduction from baseline in the % of aberrant IELs vs intestinal epithelial cells
- Histological Response: improvement from baseline in small intestinal VH:CD ratio score, Marsh score and total IEL counts
 - VH:CD ratio by validated morphometry. Includes the % of patients with histological remission (VH:CD > 2).
 - Marsh-Oberhuber classes, Marsh 0, 1, 2, 3a-c. Grouping by converting the morphometric results into Marsh classes (Mäki-Jilab converter). Includes the % of patients with histological remission (Marsh 0-1).
 - IEL: for mucosal inflammation the density of IELs/100 epithelial cells will be calculated. The analysis will also include the percentage of patients with normalization of IEL counts vs. epithelial cells (% IELs < 50%).

- Clinical response: change from baseline in symptoms,
 - BSFS and number bowel movements by day and week
 - GSRS and CeD-GSRS, by week

In general, efficacy measures which require pre- and post-treatment biopsies will be based on the PP population (at least 2 biopsies, the second at least on Week 6 or later). Continuous variables will be analyzed based on the ITT population.

Change from baseline of Immunological Response 2, VH:CD and of total IEL counts will be analyzed using the same method as for the primary endpoint.

The Marsh scores will be analyzed using a multinomial logistic regression model, where treatment group, baseline Marsh score, and a treatment group-by-baseline Marsh score interaction term will be included in the model.

The secondary variable BSFS will be analyzed by calculating daily and weekly number and type of bowel movements. The bowel movement counts will be analyzed using generalized linear mixed models with subject as random effect. The statistical model will also include treatment group, time (week) and their interaction. The change in the weekly BSFS scores will mainly be assessed with descriptive statistics, where change from the 'normal (mid-scale)' will be explored. The GSRS and the CeD-GSRS will be analyzed using a linear mixed effects repeated measures model (MMRM) with the baseline value, treatment group, time point and a time point-by-treatment group interaction term as fixed effects with an underlying correlation structure between the time points that results in the best fit for the model. Subject will be included as a random effect.

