The secondary endpoints Immunological Response 2, VH:CD ratio, Marsh score and total IEL counts will be evaluated by the change from baseline to Week 12 between the AMG 714 dose arm and the placebo arm. BSFS, GSRs and CeD-GSRs will be evaluated by comparing the change from baseline in weekly scores of AMG 714 dose arm and placebo arm.

For the purpose of this study, and in agreement with leading experts in RCD-II (Malamut *et al*, 2010; Nijeboer *et al*, 2015a, 2015b), aberrant IELs will be defined by flow cytometry as surface CD3-negative, intra-cellular CD3-positive IELs (sCD3-, icCD3+). The cut-off chosen for diagnosis of RCD-II is 20% in accordance with most recent studies (Nijeboer *et al*, 2015b). In IHC, these cells are identified as icCD3+, sCD8- and the cut-off is 50% (Nijeboer *et al*, 2015b).

In addition to this standard definition of aberrant IEL (what can be called “classic RCD-II”), it is not uncommon to observe the diagnosis of RCD-II in subjects with an atypical flow cytometric phenotype of the aberrant IELs, yet otherwise meeting the definition of RCD-II. These “Atypical RCD-II” patients may be enrolled in the study and would be part of the intent-to-treat (ITT) population as well as of the per protocol (PP) population except for the analysis of Immunological Response 1 and 2 (since the aberrant cells object of Immunological Response endpoints are different). In other words, all endpoints except Immunological Response 1 and 2 will be assessed with inclusion of any atypical subject enrolled. However, because it is possible that these patients behave differently, sensitivity analyses may also be conducted excluding the atypical subjects.

The **secondary objective** of the study is:

- To assess the safety and tolerability of AMG 714 when administered to adult patients with RCD-II.

The **safety endpoints** of the study are:

- Adverse events (AEs);
- Clinical laboratory tests;
- Physical examination;
- Vital signs;
- Immunogenicity.

Clinical laboratory tests -including immunogenicity-, physical examinations and vital signs will be tabulated by time point and treatment group and reviewed for potential safety signals. All adverse events (AEs) and serious adverse events (SAEs) will be listed and tabulated by system organ class (SOC), preferred term (PT) and further by severity and relatedness to the study drug.

The **exploratory objectives** of the study are:

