8.2.1 Definition of derived variables

Geometric mean will be calculated as:

$$\text{mean}_{\text{geo}} = \exp\left\{\frac{1}{n} \sum_{i=1}^n \ln x_i\right\}.$$

Values that are missing or not available will be ignored in calculation of geometric mean.

CV%_{geo} will be calculated using the following formula:

$$\text{CV}\%_{\text{geo}} = 100\% \cdot \sqrt{\exp V_{\ln} - 1}.$$

Values that are missing or not available will be ignored in calculation of CV%_{geo}.

Absolute change from baseline for a given treatment needs to be calculated, the following formula will be used:

$$\text{Absolute change from baseline} = \text{Post-baseline value} - \text{Pre-dose value}.$$

For weekly scores, Week 0 score is considered to be the baseline value. If Week 0 score is not available, the first non-missing result within 2 weeks of treatment will be used as baseline. For daily scores (e.g. CeD PRO), Day 0 score is considered to be the baseline; in case Day 0 score is not available, the first non-missing result within 2 weeks of treatment will be used as baseline. Otherwise, the given subject will be considered non-evaluable for the specific test. In case pre-dose value doesn't exist (i.e. for biopsy endpoints), screening value will be used as baseline.

In the case where relative (%) change from baseline needs to be calculated, the following formula will be used:

$$\text{Relative (\%) change from baseline} = (\text{Post-baseline value} - \text{Pre-dose value}) / (\text{Pre-dose value}) \cdot 100\%.$$

For weekly scores, Week 0 score is considered to be the baseline value. If Week 0 score is not available, the first non-missing result within 2 weeks of treatment will be used as baseline. For daily scores (e.g. CeD PRO), Day 0 score is considered to be the baseline; in case Day 0 score is not available, the first non-missing result within 2 weeks of treatment will be used as baseline. Otherwise, the given subject will be considered non-evaluable for the specific test. In case pre-dose value doesn't exist (i.e. for biopsy endpoints), screening value will be used as baseline.

Body mass index (BMI) is calculated using the formula:

$$\text{BMI (kg/m}^2\text{)} = \text{weight (kg)} / [\text{height (m)} * \text{height (m)}].$$

Body surface area (BSA) is calculated using Dubois' formula:

$$\text{BSA (m}^2\text{)} = 0.007184 * \text{height (cm)}^{0.725} * \text{weight (kg)}^{0.425}.$$

Table 2 Decimal places for summary statistics of continuous and categorical variables

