The modelling results (ANOVA table, parameter estimates, estimated treatment effect, marginal means estimates and results of the check of assumptions) will be tabulated and 95% confidence intervals added, where appropriate.

As a secondary assessment, the same model will be fitted using the absolute change in total IEL counts as a response variable. The modelling results (ANOVA table, parameter estimates, estimated treatment effect, marginal (i.e. least squares) means estimates and results of the check of assumptions) will be tabulated and 95% confidence intervals added, where appropriate.

The baseline and post-baseline values along with the change from baseline values both relative and absolute) will also be described by summary statistics and tabulated by treatment group. Baseline and post baseline values will also be listed.

PP population will be used for the analysis.

Change from baseline in clinical symptoms: Bristol Stool Form Scale (BSFS)

The Bristol Stool Form Scale is a pictorial aid to help subjects identify the shape and consistency of their bowel movements during the study (Riegler *et al* 2001).

Subjects will be asked to complete this form daily using an electronic diary at the time of each bowel movement from randomization through the Final Study Visit (Visit 9; Week 16/Day 112). If no bowel movements were experienced by the subject on any given day, the subject should document this using the electronic diary.

BSFS will be described by calculating daily and weekly number and type of bowel movements.

The total weekly bowel movement counts will be analysed using generalized linear mixed models with subject as a random effect. The statistical model will include as fixed effects treatment group, time (week) and their interaction. Poisson distribution with log-link will be used for modelling the counts. The following model will be fitted:

$$\log(Y_{ijk}) = \mu + \alpha_j + \gamma_k + \lambda_{jk} + \eta_i + \varepsilon_{ijk},$$

where

- Y_{ijk} is the bowel movement count for subject i ($i = 1, \dots, n_j$) from treatment group j ($j = 1, 2$) at week k ($k = 0, 1, \dots, 16$),
- μ is the overall mean on log-scale,
- α_j is the fixed effect due to treatment j on log-scale,
- γ_k is the fixed effect due to week k on log-scale,
- λ_{jk} is the fixed interaction effect due to treatment j and week k on log-scale,

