Weekly bowel movements and their BSFS types will be tabulated by treatment group and week and summarized by descriptive statistics, absolute numbers and percentages. Also, percentage of subjects with diarrhoea (at least 1 BSFS ≥ 6 for the week) and percentage of subjects with constipation (at least 3 days without bowel movement for the week) by week and by treatment group will be presented. Mean weekly bowel movement counts will also be presented graphically by time point and treatment group.

As an exploratory assessment, averages by treatment for proportion of subjects showing BSSF ≥ 6 by time will be plotted. The differences in treatment AUCs will be explored using one-way analysis of variance. These analyses will be conducted internally by Celimmune.

The daily bowel movement counts and their BSFS scores will only be listed.

ITT population will be used for the analysis as long as there is a baseline and post-treatment measure (i.e. not lost to follow-up).

Change from baseline in clinical symptoms: Gastrointestinal Symptom Rating Scale (GSRs)

The GSRs is a 15-question 7-scale questionnaire used to assess five dimensions of gastrointestinal syndromes: diarrhea, indigestion, constipation, abdominal pain and reflux (Svedlund *et al* 1988). While not specific for celiac disease, the GSRs is widely used in gastroenterology and has been used in several clinical trials of experimental medications in celiac disease, thus becoming a very useful tool with abundant existing reference data (Kelly *et al* 2013; Lähdeaho *et al*, 2011; Leffler *et al*, 2015).

Subjects will be asked to complete this questionnaire weekly, using an electronic diary, from the day of randomization through the Final Study Visit (i.e. on Visits 1 to 9).

The total GSRs score will be calculated as the mean of the scores of all 15 questions, with the scores for the individual questions between 1 (No discomfort at all) and 7 (Very severe discomfort). Therefore, the smaller the total GSRs score, the milder the symptoms of the subject.

The change from baseline in total GSRs score will be analysed using a linear mixed effects repeated measures model (MMRM) with the baseline value, treatment group, time point and a time point-by-treatment group interaction term as fixed effects with an underlying correlation structure between the time points that results in the best fit for the model. Subject will be included as a random effect. The following model will be fitted:

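### The BSFS endpoint is stated as change in weekly scores, but no weekly stool-form score is derived; the model counts stools of any form, and one loose stool sets the diarrhoea flag.

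*SAP*

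**What the plan says.** - **Stated endpoint.** SAP section 2: "BSFS, GSRs and CeD-GSRs will be evaluated by comparing the change from baseline in weekly scores of AMG 714 dose arm and placebo arm". SAP 8.2.1 adds the baseline rule: "For weekly scores, Week 0 score is considered to be the baseline value".
- **Protocol.** Section 22.6 plans a mixed model for bowel movement counts. It leaves weekly BSFS scores mainly to descriptive statistics, "where change from the 'normal (mid-scale)' will be explored". It does not say how a weekly score is formed.
- **Derivation.** SAP 8.6.2: "BSFS will be described by calculating daily and weekly number and type of bowel movements".
- **Model.** SAP 8.6.2: "The total weekly bowel movement counts will be analysed using generalized linear mixed models with subject as a random effect", and "Poisson distribution with log-link will be used for modelling the counts".
- **Form-based summaries.** SAP 8.6.2 tabulates stool types by arm and week and reports the "percentage of subjects with diarrhoea (at least 1 BSFS ≥ 6 for the week". It adds an exploratory plot of the proportion of subjects at BSFS 6 or above over time, with AUCs compared by one-way analysis of variance. Daily scores are only listed.

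**The concern.** The endpoint promises a change in a weekly score, and the SAP has a baseline rule for weekly scores, but for BSFS there is no score to which the rule can apply. GSRS and CeD-GSRS show what is missing: each has a scoring formula (the mean of 15 or 10 items) and a model for change from baseline.

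What remains for BSFS is a model that does not use form and a weekly flag with a very low threshold. Diarrhoea is the first symptom named in the RCD-II definition (Protocol 9.1, criterion 4), and BSFS is a named secondary endpoint. An improvement in consistency could go unseen in the model and be understated by the flag.

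**Working it through.** The documents give no power, effect size or expected value for BSFS, so there is no plan figure to reproduce.

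**1. Endpoint against analysis.** SAP 2 needs one BSFS value per subject per week and its change from Week 0. The visible 8.6.2 text offers the weekly count of all movements, types tabulated by arm and week, and a yes/no weekly flag. None is a per-subject weekly form score. The mid-scale summary in Protocol 22.6 does not reappear.

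**2. Count model.** The outcome is the number of movements whatever their type. If all 14 weekly stools go from watery to formed, the rate ratio is 14/14 = 1.0.

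**3. Flag, one subject.** It is positive when loose stools (BSFS 6 or above) number at least 1. At 21 loose stools it is positive; at 1 it is still positive, after a fall of 20/21 = 95%.

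**4. Flag, across subjects.** Assumed, not in the documents: n stools a week, loose share p falling from 50% to 10%, intraclass correlation ρ between a subject's stools.
- Independent stools: P(flag) = 1 − (1 − p)^n.
- Clustered stools (beta-binomial): P(flag) = 1 − Π (b + i)/(a + b + i) for i = 0 to n − 1, with a = p(1 − ρ)/ρ and b = (1 − p)(1 − ρ)/ρ.

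Example, n = 14, independent: 1 − 0.5^14 = 0.9999 and 1 − 0.9^14 = 0.771, a drop of 0.229.

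| Stools/week | Clustering | Flag at 50% loose | Flag at 10% loose | Drop (points) |
|---|---|---|---|---|
| 7 | independent | 99.2% | 52.2% | 47 |
| 7 | ICC 0.1 | 96.8% | 43.1% | 54 |
| 7 | ICC 0.3 | 89.1% | 31.4% | 58 |
| 14 | independent | >99.9% | 77.1% | 23 |
| 14 | ICC 0.1 | 99.5% | 59.6% | 40 |
| 14 | ICC 0.3 | 94.7% | 40.2% | 54 |
| 21 | independent | >99.9% | 89.1% | 11 |
| 21 | ICC 0.1 | 99.9% | 68.5% | 31 |
| 21 | ICC 0.3 | 96.6% | 45.1% | 51 |

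Drops are taken before rounding. In every row the loose share itself falls by 80% of its starting value (from 50% to 10%). The flag lags most when stools are frequent and weakly clustered.

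**5. Exploratory AUC.** One-way analysis of variance needs one AUC per subject, but the text describes an arm-level proportion and gives no time unit. On a weekly unit it would use the same one-stool rule. On a daily unit, a subject's AUC would be close to the number of days with a type 6-7 stool, which is a reasonable measure.

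**The case against.** - **The protocol chose this split.** It specifies the count model and mainly descriptive handling of scores. Frequency is also a legitimate diarrhoea measure: GSRS item 11 defines diarrhoea by too frequent emptying. This stands, and it is a reason to keep the count model. It does not supply the weekly score that SAP 2 says is compared.
- **Diarrhoea is measured elsewhere.** The GSRS diarrhoea dimension (items 11, 12 and 14) is summarised with change from baseline, CeD-GSRS includes those items and is modelled, and CeD PRO has daily diarrhoea and loose-stool items. This stands. A reader might infer that the trial would report no effect on diarrhoea; the documents do not support that. These instruments still do not deliver the BSFS endpoint.
- **The flag is descriptive and can move.** No test on the weekly percentage is specified, and with clustering or low frequency it falls by up to 58 points. Symptoms are not required at entry of previously treated or steroid-treated subjects, so high loose-stool counts cannot be presumed. It would be wrong to say that the flag generally stays positive through large improvement.
- **The stool-type table may be per subject.** One might infer that it pools movements, so that subjects with many stools dominate. The SAP does not say so: 8.2 defines its descriptive statistics by number of subjects, and the templates in Appendix 4 are given by title only.
- **Part of the section is not visible.** The text available breaks off within the list of model terms and resumes at the tables. The modelled variable is stated before the break, but a further derivation there cannot be excluded.

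**Conclusion.** The point holds as a gap between the stated endpoint and its analysis. SAP 2 commits to change in weekly BSFS scores, and no visible text in 8.6.2 defines one. Two consequences need no assumption: the count model gives a rate ratio of 1.0 when form normalises at constant frequency, and one loose stool keeps a subject in the diarrhoea percentage for that week.

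The size of the flag's lag does rest on assumptions. For a fall in loose share from 50% to 10% it drops by 11 to 47 points with independent stools at 21 to 7 a week, and by 31 to 58 points with ICC 0.1 to 0.3.

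The documents do not establish that the exploratory AUC saturates; its time unit is undefined, and the issue arises only if that unit is the week. Nor do they require a form-based variable to displace the protocol's count model as the lead BSFS analysis. The primary endpoint is not affected.

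**What to change.** Before unblinding, amend SAP 8.6.2 as follows.

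1. Derive for each subject and week the number of type 6-7 stools per recorded diary day, or the percentage of stools that are type 6-7. State which diary days form Week 0, since the diary opens at Visit 1.
2. Compare arms on the change in that variable from Week 0, alongside the protocol-specified total-count model.
3. Report days per week with a type 6-7 stool beside the one-stool flag, or in its place.
4. Use that per-subject variable for the exploratory plot and AUC, and state the time unit.

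The diary already records every movement and days without one, so no new data are needed. The cost is SAP wording, one derived variable and one more table.

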where $\mu_{AMG\ 714}$ and $\mu_{placebo}$ denote the mean baseline to Week 12 relative (%) change in % aberrant IELs vs total IELs as assessed by flow-cytometry in the AMG 714 and placebo arm, respectively. The hypotheses will be tested using a two-sided, 0.10 level of significance.

7 Estimation of sample size

The CELIM-RCD-002 study is an exploratory proof-of-concept (POC) study of an experimental medication, AMG 714, in RCD-II patients. While it will be the first such study sponsored by a pharmaceutical company, the straightforward design is based on several academic studies (Goerres *et al*, 2003; Brar *et al*, 2007; Tack *et al*, 2011a, 2011b) as well as on the nonclinical proof-of-principle signal obtained with AMG 714 in intestinal explants from patients with RCD-II (Malamut *et al*, 2010).

The sample size is based on the size of previous academic studies. Published prospective academic studies have ranged from 13 to 18 subjects total (Tack *et al*, 2011a, 2011b) and CELIM-RCD-002 will be the largest prospective trial ever conducted in RCD-II, a very rare malignant disease.

The sample size of 24 subjects (16 subjects in AMG 714 arm and 8 subjects in placebo arm) has been calculated to achieve at least ~ 80% power to detect a 20 percentage point difference in the primary endpoint, the difference in the baseline-to-Week 12 reduction of % aberrant IELs vs total IELs between the AMG 714 arm and placebo arm.

This sample size calculation was based on the following assumptions:

- Two-sided type one error rate $\alpha = 0.1$.
- Power $1-\beta = 0.8$.
- Analysis method: one-way analysis of variance (ANOVA) by SAS[®] (proc power).
- 2:1 allocation ratio between the AMG 714 and placebo arms.
- Common SD = 17.4 for the baseline to Week 12 reduction in % aberrant IELs as assessed by flow-cytometry.

- Mean change of 20 percentage points and 0 percentage points in the baseline to Week 12 reduction in % aberrant IELs in the AMG 714 and placebo arms, respectively.

The standard deviation used for the sample size calculation is computed from the % aberrant IELs (obtained by flow-cytometry) data from 13 subjects treated with cladribine (subset of the subjects reported in Tack et al, 2011).

8 Statistical methods

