8.2 General statistical considerations

Descriptive statistics (e.g. mean, median, standard deviation (SD), minimum (MIN), maximum (MAX), and number of subjects with an observation (N) or missing observation (NMISS)) are used for summarizing continuous variables. Additional statistics will be provided for PK-related data, including the geometric mean, SD of log-transformed data, geometric CV% and geometric N (i.e. number of subjects with an observation that are included in the natural logarithmic transformation).

Frequencies and percentages are used for summarizing categorical variables.

All summary statistics will be presented by treatment arm and if repeated measures, then by visit/collection time point.

All listings will be created using ITT population. The PP and ITT flags for each subject will be included in all listings.

All tests will be two-sided, if not stated differently. P-values smaller than 0.1 (for primary hypothesis) or 0.05 (all other hypotheses) will be considered statistically significant. In addition to the inferential statistics, 90% or 95% confidence intervals will be constructed. For the primary endpoint a 90% confidence interval of the treatment difference will be

constructed. Ninety-five percent (95%) confidence intervals will be constructed for the individual treatment point estimates.

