$$Y_{ijk} = \mu + \alpha_j + \gamma_k + \lambda_{jk} + \beta \cdot \text{baseline GSRs}_{ij} + \eta_i + \varepsilon_{ijk},$$

where

Y_{ijk} is the absolute change from baseline in total GSRs score for subject i ($i = 1, \dots, n_j$) from treatment group j ($j = 1, 2$) at week k ($k = 1, 2, \dots, 16$),

μ is the overall mean,

The baseline and post-baseline total GSRS scores along with the change from baseline values will also be described by summary statistics and tabulated by treatment group. In addition to that, the baseline and post-baseline scores of all 15 questions and for the mean total scores of five dimensions of gastrointestinal syndromes (diarrhoea (questions 11, 12 and 14), indigestion (questions 6-9), constipation (questions 10, 13 and 15), abdominal pain (questions 1, 4 and 5) and reflux (questions 2 and 3)) along with the change from baseline values will be described by summary statistics and tabulated by treatment group. Both the scores of individual questions and the total GSRS scores will also be listed. Mean total GSRS scores as well as the scores of the individual questions, will also be presented graphically by time point and treatment group.

ITT population will be used for the analysis as long as there is a baseline and post-treatment measure (i.e., not lost to follow-up).

Change from baseline in clinical symptoms: the celiac disease GSRS (CeD-GSRS)

The CeD-GSRS is formed by the subset of questions from GSRS questionnaire (questions 1, 4-9, 11, 12 and 14).

The total CeD-GSRS score is calculated as the mean of scores of all 10 questions in CeD-GSRS questionnaire, with the scores of the questions between 1 (No discomfort at all) and 7 (Very severe discomfort). Therefore, the smaller the total CeD-GSRS score, the milder the symptoms of the subject.

The change from baseline in CeD-GSRS will be analysed using a linear mixed effects repeated measures model (MMRM) with the baseline value, treatment group, time point and a time point-by-treatment group interaction term as fixed effects with an underlying correlation structure between the time points that results in the best fit for the model. Subject will be included as a random effect. The following model will be fitted:

$$Y_{ijk} = \mu + \alpha_j + \gamma_k + \lambda_{jk} + \beta \cdot \text{baseline CeD GSRS}_{ij} + \eta_i + \varepsilon_{ijk},$$

where

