Y_{ijk} is the absolute change from baseline in total CeD-GSRS score for subject i ($i = 1, \dots, n_j$) from treatment group j ($j = 1, 2$) at week k ($k = 1, 2, \dots, 9$),

μ is the overall mean,

α_j is the fixed effect due to treatment j ,

γ_k is the fixed effect due to time point k ,

λ_{jk} is the fixed interaction effect due to treatment j and time point k ,

β is the parameter estimate of the baseline total CeD-GSRS score,

η_i is the random effect due to subject i ,

ε_{ijk} is the random error for subject i from treatment group j for time point k .

Due to the repeated structure of the data, the measurements within a subject will be correlated. Therefore, it is assumed that the overall covariance matrix of the response is block-diagonal. In order to determine the covariance structure that best fits the data, the same model with different covariance structures is fitted. Initially, models will be fit

assuming unstructured (UN) variance-covariance structure. Common within and between treatment variance components (compound symmetry (CS), first-order autoregressive (AR(1)) and Toeplitz covariance structures) will be further explored to increase sensitivity of statistical tests. The best model will be chosen by comparing the Akaike Information Criterion (AIC) of the models with different covariance structures.

The following SAS program will be used for carrying out the analysis:

```
proc glimmix data=ced_gsrs;
  class subjid trt week (ref=FIRST);
  model ced_gsrs = ced_gsrs_b1 trt week trt*week / solution;
  random _residual_ / subject=subjid type=UN;
  estimate "AMG 714 vs Placebo" trt 1 -1 /alpha=0.05 cl;
  estimate "Week 1: AMG 714 vs Placebo" trt 1 -1
    trt*week 0 0 0 0 0 0 0 0 0 0 0 0 0 0 0 0 1
    0 0 0 0 0 0 0 0 0 0 0 0 0 0 0 -1 /alpha=0.05 cl;
  estimate "Week 2: AMG 714 vs Placebo" trt 1 -1
    trt*week 1 0 0 0 0 0 0 0 0 0 0 0 0 0 0 0 0
    -1 0 0 0 0 0 0 0 0 0 0 0 0 0 0 0 /alpha=0.05 cl;
  ...
  estimate "Week 16: AMG 714 vs Placebo" trt 1 -1
    trt*week 0 0 0 0 0 0 0 0 0 0 0 0 0 0 0 1 0
    0 0 0 0 0 0 0 0 0 0 0 0 0 0 0 -1 0 /alpha=0.05 cl;
  lsmeans trt /alpha=0.05 cl;
  lsmeans trt*week /alpha=0.05 cl;
ods output CovParms=Cov_Par LSMeans=LS_est Estimates=Eff_est
  FitStatistics=Fit_Stat ParameterEstimates=Par_est
  Tests3=Type_3;
run;
```

Note that the value of `type` will be changed according to which covariance structure is being fitted.

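### The CeD-GSRS program omits the random subject effect in the written model, so an AIC choice of AR(1) can raise the week-averaged treatment test to about 7-11% at a nominal 5%

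*SAP*

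**What the plan says.** For both GSRS and CeD-GSRS, SAP 8.6.2 specifies a mixed model for change from baseline. It has baseline, treatment, time point and their interaction, a random subject effect (the term eta_i in each equation), and errors "with an underlying correlation structure between the time points that results in the best fit for the model". Protocol 22.6 states the same rule.

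For CeD-GSRS the SAP adds detail. It starts from an unstructured covariance, then explores compound symmetry, AR(1) and Toeplitz with the stated purpose of making the tests more sensitive. It ends: "The best model will be chosen by comparing the Akaike Information Criterion (AIC) of the models with different covariance structures". The only covariance statement in the program is "random _residual_ / subject=subjid type=UN", and a note says that the value of `type` changes with the structure being fitted. There is no subject-intercept statement, degrees-of-freedom option or robust standard error. The program estimates an overall AMG 714 versus placebo contrast and one contrast per week up to Week 16, whereas the CeD-GSRS equation indexes weeks 1 to 9. The GSRS equation indexes weeks 1 to 16.

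SAP 8.2 sets the level: "All tests will be two-sided, if not stated differently" and "P-values smaller than 0.1 (for primary hypothesis) or 0.05 (all other hypotheses) will be considered statistically significant". If parametric assumptions fail, a GEE analysis is added; no trigger is defined.

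**The concern.** For three of the four candidates, leaving out eta_i does little harm. Unstructured, compound symmetry and Toeplitz can all represent a correlation that persists between distant weeks of the same patient. AR(1) cannot: its correlation decays geometrically to zero. It is the one candidate for which the written model and the program differ in substance.

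The week-averaged contrast depends mainly on that long-lag correlation, because its standard error is governed by how much patients' 16-week averages vary. If AR(1) is fitted without an intercept and patients do keep their own symptom level, chance differences between 16 and 8 patients are partly read as a treatment effect. A symptom benefit could then be declared too often, with an interval that is too short.

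**Working it through.** **The plan's own figure.** The documents state no operating characteristic for GSRS or CeD-GSRS beyond the nominal 0.05. The one design figure is primary-endpoint power of about 80% (SAP 7). With 16 and 8 subjects, difference 20, SD 17.4 and two-sided alpha 0.10, the noncentrality is 20 / [17.4 × √(1/16 + 1/8)] = 20 / 7.53 = 2.65. On 22 df the power is 82.3%, so the figure is reproduced. It does not bear on this point beyond fixing the sample size.

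**Why AIC favours AR(1).** At 16 weeks the covariance parameter counts are 2 (compound symmetry), 2 (AR(1)), 16 (Toeplitz) and 16 × 17 / 2 = 136 (unstructured). The AIC penalty is twice the count: 4, 4, 32 and 272. Toeplitz must therefore improve −2 log-likelihood by more than 28 to beat AR(1), and unstructured by more than 268. Compound symmetry has no such handicap but cannot represent serial decay.

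**Why that matters.** Suppose the patient effect holds a share tau = 0.4 of the variance and the rest is AR(1) with rho = 0.5. Before baseline adjustment, adjacent weeks correlate 0.4 + 0.6 × 0.5 = 0.70. Weeks 12 apart correlate 0.4 + 0.6 × 0.5^12 = 0.40. An AR(1) matched at lag 1 gives 0.70^12 = 0.01.

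**Null simulation.** Inputs from the documents: 16 versus 8 patients, baseline plus 16 weekly scores, the four candidates, lowest AIC, two-sided 5%. Assumed, because the documents give no GSRS correlations: tau, rho and an optional share of independent weekly noise; complete, normal data. All structures were fitted by REML and the week-averaged contrast was tested against t on 24 − 2 − 1 = 21 df. There were 3,000 trials per row, with Monte Carlo SE about 0.4-0.6 points.

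| tau | rho | noise | AR(1) chosen | Rejects, AIC as coded | Rejects, intercept + AR(1) | Rejects, AIC with intercept + AR(1) added |
|---|---|---|---|---|---|---|
| 0.4 | 0.5 | 0 | 79% | 10.2% | 4.9% | 5.2% |
| 0.3 | 0.5 | 0 | 86% | 9.8% | 5.0% | 5.7% |
| 0.6 | 0.5 | 0 | 63% | 9.8% | 5.0% | 5.1% |
| 0.5 | 0.7 | 0 | 94% | 8.1% | 5.2% | 6.1% |
| 0.3 | 0.7 | 0 | 96% | 7.0% | 5.1% | 6.0% |
| 0.4 | 0.7 | 0.15 | 50% | 8.8% | 5.1% | 5.4% |
| 0.5 | 0.2 | 0 | 6% | 5.4% | 4.6% | 4.6% |
| 0.5 | 0.1 | 0 | 0.4% | 4.7% | 4.7% | 4.7% |
| 0.5 | 0 | 0 | 0% | 4.6% | 4.6% | 4.6% |
| 0 | 0.5 | 0 | 97% | 3.9% | 3.1% | 3.8% |

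- Fixed unstructured (4.8-5.5%) and fixed Toeplitz (4.6-5.6%) also hold the level.
- A wider grid of 1,500 trials per setting gave 7.4-11.1% where both features were present. It included tau 0.5, rho 0.3: AR(1) chosen in 23%, rejection 8.5%. That batch ran about a point high throughout (fixed unstructured rejected 6.1-6.6%), so the 3,000-trial figures are the better guide.
- A separate simulation of 940 trials at tau 0.4, rho 0.5, without the unstructured candidate, gave AR(1) in 79% and rejection of 10.2%, against 5.3% with intercept plus AR(1).
- A large-sample reference in place of 21 df gave 8.7-12.0% in the first six rows.

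**Nine time points** (2,000 trials): AR(1) chosen in 86-92%, rejection 5.4-6.3%.

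**Single weeks** (AR(1) forced, 16 weeks, 1,500 trials): the Week 12 contrast rejected in 4.9-5.7% and the last week in 6.1-6.5%.

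**The case against.** The strongest reply is that the SAP already specifies the right model. The text and equation contain eta_i, and the same model is to be refitted under each structure, so choosing AR(1) would mean eta_i plus AR(1), which holds about 5%. SAP 8.6.1 also lets SAS code be modified without an amendment. This stands in part. The text and program disagree, and the program is where the inflation arises. It does not clear the plan: the SAP says this program will be used and that only `type` changes. Freedom to edit code leaves the intercept undecided and does not require the decision to be made blind.

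A reader might infer that AIC selection is itself at fault. The last column of the table does not support that: keeping AIC but adding intercept plus AR(1) to the candidates gives 4.6-6.1% when patients differ persistently. The rule is also pre-specified and ranks covariance fit, not the treatment p-value.

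A reader might also infer that persistent patient differences are enough. They are not. With rho of 0 to 0.1, AIC picks compound symmetry in 92-97% of trials and the level is about 5%.

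SAP 2 describes the evaluation as a comparison of weekly scores, and the Week 12 contrast is near nominal. That narrows the point to the week-averaged contrast. The GEE fallback offers little protection, being additional and without a trigger.

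**Conclusion.** The point holds in a limited form. As coded, the week-averaged CeD-GSRS test can run at about 7-11% instead of 5%, so a nominal 95% interval covers about 89-93%. This needs persistent patient differences, serial correlation of about 0.3-0.7 on top of them, and 16 weekly scores. These correlations are assumptions, and other values give other rates. Sixteen weeks is the better reading of the plan, since the program, the GSRS equation and weekly collection through Visit 9 agree on it; at nine time points the rate is about 5-6%.

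For GSRS the written model and best-fit rule are the same, but its program is not visible in the text reviewed, so the same defect is likely, not shown. The weekly CeD PRO program looks similar but was not tested, and nothing is claimed about it. These are secondary endpoints in an exploratory study. The primary ANCOVA is unaffected, as is the go/no-go rule in Protocol 13.1, which rests on the two immunological responses. The change is worth making before unblinding, but it is not critical to the trial's main conclusion.

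**What to change.** In SAP 8.6.2, for CeD-GSRS and GSRS, before unblinding:

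1. Make the program match the written model. Add `random intercept / subject=subjid`, keep an AR(1) residual, and state a small-sample degrees-of-freedom method such as Kenward-Roger. Name this as the reported analysis. The simulations used t on 21 df, so Kenward-Roger itself was not checked.
2. Keep unstructured, compound symmetry, AR(1) alone and Toeplitz as sensitivity fits. If AIC selection is retained, at least add intercept plus AR(1) to the candidates.
3. Reconcile weeks 1 to 9 in the CeD-GSRS equation with the Week 16 contrasts in the program.
4. Check the weekly CeD PRO model separately before extending the change to it.

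The cost is one statement, one option and a few sentences of SAP text. Intervals become slightly wider, and the test is mildly conservative (3.1% in the simulation) if there is no persistent patient effect. Fixing unstructured or Toeplitz would also hold the level; intercept plus AR(1) is preferred because it follows the equation already written.
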